2.1.5 Safety Objective

Assess the safety impact of treatment with RHB-104.

2.2 Outcomes/Endpoints

The outcome endpoints for summaries by treatment from the parent study (RHB-104 treatment and Placebo) and overall are grouped into 4 families based on level of objectives: (i) primary endpoint; (ii) key secondary endpoint; (iii) selected other secondary endpoints; and (iv) selected other endpoints.

2.2.1 Primary Endpoint/Variable: Remission

In general use of rescue medication is considered as treatment failure (not achieving remission or response) if there are any new use of rescue medication to treat CD or increased rescue medication dose from baseline prior to any remission or response assessment. Please refer to section 6.1.6 for more details.

The primary variable is the proportion of subjects who experienced remission at Week 16 after the initiation of open-label phase, where remission is defined as a subject having a Crohn's Disease Activity Index (CDAI) score of <150 . Subjects who have a Week 16 CDAI measurement ≥ 150 or who do not have a CDAI measurement at Week 16 will be classified as not having achieved remission at that time point. Initiation of open-label phase is the first dosing time of open-label phase and from here and after it would be reference as initiation.

The CDAI is used to assess the activity of CD; higher scores indicate more active disease.

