3. STUDY DESIGN

This is an open label, multicenter, Phase III, study designed to evaluate the efficacy and safety of RHB-104 to treat subjects with active CD as defined by CDAI \geq 150 despite 26 weeks of treatment with study drug in RedHill Biopharma Study RHB-104-01. RHB-104 consists of 3 antibiotics with activity against *Mycobacterium avium subsp. Paratuberculosis* (MAP), a potential cause of CD. Eligible subjects with active CD who have completed 26 weeks of study drug as part of the RHB-104-01 study will receive up to 52 weeks of open label RHB-104. Subjects enrolled in the open label study may have current CD therapies adjusted or withdrawn as clinically indicated by their local investigator after 8 weeks of open label RHB-104 treatment. Sites should begin tapering steroids upon completion of 4 weeks of RHB-104 treatment with the goal of being steroid free by week 14 – Refer to Appendix 13 of protocol.

MAP are slow growing mycobacteria without a proven antibiotic treatment, and the duration of antibiotic treatment required to achieve remission in subjects with CD caused by MAP is believed to be approximately 16-26 weeks. Subjects with response at week 26 may ultimately achieve remission at a later time point with continued treatment for MAP. Similarly, some subjects may achieve response or achieve remission prior to week 26. This study is designed to assess response, remission, and maintenance of remission in subjects on open label RHB-104 through week 52, as well as corticosteroid free remission at week 16.

Blood samples will be collected at Screening and at every visit after the initial 8 weeks of treatment to test for MAP in the serum using a polymerase chain reaction (PCR) assay. Similarly, MAP cultures will be prepared from whole blood collected at Screening and at weeks 16, 26 and 52.

Safety of the fixed-dose combination product, RHB-104, will also be assessed.

Colonoscopy will be done in consenting subjects at baseline and after 16 and 52 weeks of open label RHB-104 to assess for mucosal healing as well as MAP status via PCR and culture.

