6.1.6 Rescue Medications Use

Subjects rescued with the following treatments or whose baseline doses/regimens are increased to treat new or unresolved CD symptoms may remain on the study drug at the discretion of the investigator and continue to be assessed at all scheduled study visits:

- Oral or rectal 5-ASA compounds
- Azathioprine or 6-mercaptopurine (6-MP) or methotrexate
- Total parenteral nutrition as treatment of CD
- Systemic or rectal corticosteroid therapy
- Anti-TNF or other biologic agent

In analyses of remission or response, subjects who initiate new treatment or increase concomitant medication to treat CD symptoms will be considered as treatment failures.

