6.2.6.2 Crohn's Disease History

Crohn's disease history is recorded at screening on the history eCRF per subject data migration from the parent study (please refer to Appendix for details). Data including steroid status (steroid-refractory disease or steroid-dependent disease) will be presented descriptively by parent study treatment group and overall and also presented as data listing. Duration of each condition is based on the first dose of study medications administration for the current extension study.

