All prior and concomitant medications recorded on CRF will be mapped to standardized terms using the World Health Organization Drug Dictionary coding system (WHO DD). The Anatomical–Therapeutic–Chemical (ATC) Classification level 2 and preferred term will be used to summarize the data by treatment group. A subject having the same medication more than once will be counted only once in the incidence table for that medication. For each ATC classification and Preferred Term the number and percentage of subjects will be displayed. Summary tables will be presented on SAF population separately for the following:

- Prior Medications Use for Crohn’s Disease
- Prior Medications Use
- Concomitant Medications Use
- Prior Biological Agents Use
- Concomitant Medications Use for Crohn’s Disease
- Prior Steroids Use
- Concomitant Steroids Use
- Concomitant Steroids Use for Crohn’s Disease
- Prior Antineoplastic, Immunosuppressive and Biologic Use
- Concomitant Antineoplastic, Immunosuppressive and Biologic Use

All prior and concomitant medications/treatments will be presented in a data listing with dose, units, frequency, route of administration, indication, start and end dates for the safety population. A separate Steroids use subject listing may be presented providing the steroid coded ATC classification, preferred term, and date.

Any concomitant procedures recorded on CRF will be presented in a data listing with procedure name, date and reason.

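### The treatment-failure rule in SAP 2.2.1 and 6.1.6 does not settle its reference dose for a Crohn's drug tapered and then raised again before week 16

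*SAP*

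**What the plan says.** SAP 2.2.1 introduces the rule as a general one. Failure, for remission and for response, follows from "any new use of rescue medication to treat CD or increased rescue medication dose from baseline prior to any remission or response assessment". It then sends the reader to 6.1.6.

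SAP 6.1.6 lists the rescue treatments, including systemic or rectal corticosteroids. Two of its sentences bear on the reference dose:

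- The opening sentence concerns who may continue. Subjects given a listed treatment, or "whose baseline doses/regimens are increased to treat new or unresolved CD symptoms may remain on the study drug" at the investigator's discretion.
- The closing sentence is the analysis rule: "subjects who initiate new treatment or increase concomitant medication to treat CD symptoms will be considered as treatment failures". It gives neither a reference dose nor a time limit.

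SAP section 3 builds dose reductions into the design. On steroids: "Sites should begin tapering steroids upon completion of 4 weeks of RHB-104 treatment with the goal of being steroid free by week 14". On other treatment, subjects "may have current CD therapies adjusted or withdrawn as clinically indicated by their local investigator after 8 weeks" of open-label drug. The same section says the study will assess remission, response and maintenance, "as well as corticosteroid free remission at week 16".

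**The concern.** A failure rule tied to the baseline dose and one tied to any increase agree while doses only stay level or rise from baseline. They can differ once a dose has been lowered, and this plan asks for steroids to be lowered between week 4 and week 14, just before the week 16 assessment. Two analysts, one applying 2.2.1 and the other the closing sentence of 6.1.6, could then classify the same subject differently.

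The rule feeds the primary endpoint (week 16 remission) and the key secondary endpoint (week 16 response), including the Fisher comparisons by parent-study arm. The primary objective is to estimate one rate, so the classification rule is part of what is being estimated. Left open, the choice could be made after the data are seen. If the baseline reading is adopted, a subject whose symptoms were treated by raising steroids before week 16 can count as a remitter, and no planned rate would separate such subjects.

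**Working it through.** **Assumption.** SAP 6.1.2 defines baseline for assessments and does not mention medication doses. I take the baseline dose to be the dose in use at first open-label dosing. Only changes made to treat Crohn's symptoms between then and week 16 are considered.

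**Step 1: the texts side by side.**

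| Course of a listed drug before week 16 | 2.2.1 as written | 6.1.6 closing sentence as written | 6.1.6 closing sentence read with its opening sentence |
|---|---|---|---|
| Drug not used at baseline is started | Failure | Failure | Failure |
| Raised above baseline dose | Failure | Failure | Failure |
| Lowered but not stopped, then raised to or below baseline dose | Not failure | Failure | Not failure |
| Stopped, then restarted at or below baseline dose | Depends on whether a restart is new use; undefined | Failure on a plain reading | Depends on the same undefined term |
| Lowered and not raised again | Not failure | Not failure | Not failure |

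The third row is the clear divergence. The fourth is a gap in the definition.

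**Step 2: one subject.** Steroid at 20 mg at first dose, tapered to 5 mg, raised to 15 mg at week 12 for symptoms, CDAI 140 at week 16. Since 15 is below 20 and the drug was never stopped, 2.2.1 finds no failure, and 140 < 150 gives remission. Since 15 is above 5 and the rise was for symptoms, the closing sentence of 6.1.6 gives failure.

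**Step 3: direction.** In the table, every certain failure under 2.2.1 is also a failure under the closing sentence of 6.1.6, but not the reverse. The week 16 rates under 2.2.1 are therefore equal to or higher than those under the literal closing sentence.

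**Step 4: the plan's own precision figure.** SAP 6.1.7 uses N = 100, 50% successes and a two-sided 95% Clopper-Pearson interval. The limits are the 0.025 quantile of Beta(x, n − x + 1) and the 0.975 quantile of Beta(x + 1, n − x). For x = 50 and n = 100 they are 0.3983 and 0.6017, a width of 0.2034. This reproduces the stated 0.203 (half-width 10.15 points), which does not depend on the failure rule.

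**Step 5: effect per subject.** 1/100 = 1.0 percentage point for each subject in the third row with week 16 CDAI below 150. As an illustration, suppose 2.2.1 gives 30 remitters in 100. Both this count and the numbers reclassified are assumed.

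| Subjects reclassified | Rate | 95% interval |
|---|---|---|
| 0 | 30% | 21.2 to 40.0% |
| 1 | 29% | 20.4 to 38.9% |
| 3 | 27% | 18.6 to 36.8% |
| 5 | 25% | 16.9 to 34.7% |
| 10 | 20% | 12.7 to 29.2% |

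**Step 6: a ceiling for steroids.** Let s be the share on steroids at first dose, r the share of those raised again before week 16, and q the share of those with week 16 CDAI below 150. The documents give none of them. With assumed ranges of 20–40%, 10–30% and 30–50%:

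- low: 100 × 0.20 × 0.10 × 0.30 = 0.6 points
- high: 100 × 0.40 × 0.30 × 0.50 = 6.0 points

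For any given s, r and q the product is only an upper bound on the steroid part of the difference. The share r includes subjects raised above baseline, who fail under both texts, and subjects restarted from zero, who may. The product leaves out the other listed drugs. The true difference is zero if nobody falls in the third or fourth row.

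**Step 7: steroid-free remission.** The aim in section 3 has no counterpart among the endpoints in 2.2, the analyses in 6.3 or the tables in 8.1. The visit schedule in 4.1.1 does collect steroid status at week 16.

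**The case against.** A reader might infer that the SAP sets two competing reference doses. The documents do not support that. SAP 6.1.6 names no second reference dose; the only one in that section is baseline, in its opening sentence, as in 2.2.1. The closing sentence can fairly be read as shorthand for the category just described, and 2.2.1 defers to 6.1.6, so the two sections are not independent rules. This stands: the finding is an ambiguity, partly within 6.1.6 itself. It does not remove the problem. The opening sentence governs who may stay on drug, only the closing one governs analysis, and that one omits the reference.

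A reader might also infer that every subject raised again after the taper fails only under 6.1.6. That is not shown. The taper aims at zero, and a restart from zero may be new use under 2.2.1 and so fail under both. The clear case needs a partial taper.

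A third inference would be a bias of several points. The shares behind that range are assumed, and the product is a ceiling for steroids only.

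Other points have some force. The disease-history item, "steroid status (steroid-refractory disease or steroid-dependent disease", makes symptoms returning on taper plausible but does not show who was on steroids at first dose. Protocol Appendix 13, on the taper, is not among the documents and may cover returning symptoms; neither 2.2.1 nor 6.1.6 refers to it. Concomitant steroid use for Crohn's disease is to be summarised, and steroid use and remission are to be listed, so a reader could find affected subjects by hand. No planned table crosses the two. Finally, whether a rise that stays below baseline is a failure is a clinical choice. Either answer is defensible if stated.

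**Conclusion.** The concern holds as an ambiguity in the reference dose of the failure rule for week 16 remission and response. The classification clearly differs only for a listed drug lowered but not stopped, then raised for symptoms to or below its baseline dose before week 16, in a subject who otherwise meets the endpoint. How a restart after a full taper counts is undefined. Nothing in the available protocol text or in SAP 6.5 resolves either case.

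The only size the documents support is 1 percentage point on the primary rate per affected subject at N = 100. The number affected is unknown and may be zero. Where the readings differ, 2.2.1 gives the higher rate. This rests on taking the dose at first open-label dosing as baseline and on restricting attention to changes made for Crohn's symptoms.

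The missing rate of remission without corticosteroids is a separate gap, present whichever reference dose is chosen. Both are low-cost improvements and do not invalidate the design.

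**What to change.** 1. State one rule in both 2.2.1 and 6.1.6: from first dose to the assessment, any start, restart or increase of a listed treatment for Crohn's symptoms is failure, judged against the dose just before the change. This also gives 6.1.6 the time limit it lacks.
2. Show the week 16 remission and response rates under the above-baseline reading as a sensitivity row, stating how a restart after a full taper is classified there.
3. Separately, add the week 16 rate of remission without corticosteroids, using the steroid status collected at that visit.

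If the sponsor prefers the above-baseline rule as primary, it should say so in both sections, define how a restart counts, and make the stricter rule the sensitivity row.

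The cost is a sentence in each of two sections and a few table rows. No new data are needed: SAP 6.2.7 already plans a "data listing with dose, units, frequency, route of administration, indication, start and end dates". Two downsides remain. Reported rates may be slightly lower under the stricter rule, and each dose change needs medical review to confirm that it was made for Crohn's symptoms.

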2.2.2 Key Secondary Endpoint/Variable

The key secondary variable is the proportion of subjects who experienced response at week 16 after initiation, where response is defined as reduction from baseline of ≥ 100 in CDAI score. Subjects who have a change from baseline to week 16 in CDAI score which is not a reduction of ≥ 100 or who do not have a change from baseline to week 16 in CDAI score will be classified as not having experienced response at that time point.

2.2.3 Selected Other Secondary Endpoints/Variables

- Time to remission – Number of weeks after initiation that a subject first records a state of remission (CDAI score < 150). It will be calculated as the date on which remission is first observed minus the date of the first dosing date plus 1 day, divided by 7. For subjects still on study and not achieved remission at the time of assessment, time to remission will be censored at the date of the last assessment of CDAI score.
- Duration of remission – The number of weeks the subject is in remission (CDAI score < 150). It will be calculated as the first date following remission at which CDAI is ≥ 150 minus the date of remission, plus 1 day, divided by 7. Those subjects who experienced remission and continue to be in remission at the time of their last CDAI assessment will be censored at the date of their last CDAI assessment. Duration of remission will be calculated only for patients achieving remission.
- Time to response – Number of weeks after initiation that a subject first achieves a state of response (a reduction from baseline of ≥ 100 in CDAI score). It will be calculated as the date on which response is first observed minus the date of the first dose, plus 1 day, divided by 7. For those subjects who have not experienced response, time to response will be censored at the date of the last assessment of CDAI score.
- Duration of response – Time in weeks that a subject is in a state of response (a reduction from baseline of ≥ 100 in CDAI score). It will be calculated as the first date following response at which the reduction from baseline in CDAI is < 100 minus the date of response, plus 1 day, divided by 7. Those subjects who experienced response and continue to be in response at the time of their last CDAI assessment will be censored at the date of their last CDAI assessment. Duration of response will be calculated only for patients achieved response.
- Proportion of subjects experienced maintenance of remission (CDAI score < 150) from week 16 through week 52. Subjects experiencing a CDAI score ≥ 150 at any visit time point assessment between week 16 and week 52 or have no CDAI measurement week 16 or week 52 will be considered as having not achieved maintenance of remission.

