2.1.3 Selected Other Secondary Objectives

1. To estimate the average duration of remission among participants.
2. To estimate the average time to first response among participants.
3. To estimate the average duration of response among participants.
4. To estimate the proportion of participants who maintain a state of remission from week 16 through week 52.

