4.1.1 Study Visit Schedule

	Screening / Opt Screening / Visit Week 26 of RHB-104-01	Baseline Day 1 / Week 0 ²	Week 2	Week 4	Week 8	Week 16	Week 26	Week 39	Week 52	Week 56
Study Visit Window	(up to 21 days before BL if initial colonoscopy is performed)	Up to 21 days post SCR	± 3 days	± 3 days	± 7 days	± 7 days	± 7 days	± 7 days	± 7 days	± 7 days
Informed Consent	X									
Inclusion/ Exclusion Criteria Demography, Medical History	X	X								
Concomitant Medications Assessment		X ³	X	X	X	X	X	X	X	X
Vital Signs and Physical Exam.	X ¹	X	X	X	X	X	X	X	X	X
Adverse Event Assessments		X ³	X	X	X	X	X	X	X	
Diary Dispensing (AE/ConMed)		X	X	X	X	X	X	X	X	X
Steroid Status		X				X	X	X	X	X
CDAI assessment	X ¹				X	X	X	X	X	X
CDAI Diary Dispensing ⁴					X	X	X	X	X	
Subject Assessments: IBDQ and SF-36	X ¹					X	X		X	
Uveitis Assessment	X ¹		X	X	X	X	X	X	X	X
ECG ¹⁰	X ¹			X		X			X	X
Hematology and Biochemistry	X ¹		X	X	X	X	X	X	X	X
Urinalysis ¹¹	X ¹		X	X	X	X	X	X	X	X
C-Reactive Protein (CRP)	X ¹					X	X	X	X	
MAP Testing Blood (PCR) with Add'l Sample for Future Use	X ¹				X	X	X	X	X	X
MAP culture from blood	X ¹					X	X		X	
Fecal calprotectin	X ¹					X	X		X	
C. difficile Testing	X ¹						X		X	
Pregnancy Test Urine	X ¹	X	X	X	X	X	X	X	X	X
Optional Colonoscopy and CDEIS/SES-CD; store images		X ⁴				X ⁵			X ⁶	
IWRS Entry		X ⁷		X ⁸			X ⁹			
Study Drug Dispensing		X	X	X	X	X	X	X		
Dispensing of Drug Administration Instructions ¹²		X	X							
Drug Return & Accountability		X ¹³	X	X	X	X	X	X	X	
Review of stool sampling technique					X	X		X		
Telephone reminder of dose escalation		Day 7	Day 21							

¹ Procedure performed as part of RHB-104-01

² Baseline visit should be scheduled once the RHB-104-01 Wk26 / RHB-104-04 Screening CDAI score has been calculated (using RHB-104-01 Wk26 hematoctrit value).

³ Ongoing AEs/ConMeds from RHB-104-01 should be captured in RHB-104-04 eCRF (AEs & ConMeds for RHB-104-01 are captured in -01 eCRF up to day prior to -04 BL)

⁴ The colonoscopy must be performed on or before the Baseline or Week 0 Visit and must not interfere with CDAI data collection. If applicable, biopsies may be collected as part of the RHB-104-01 study.

⁵ In consenting subjects, colonoscopy must be performed up to 14 days after Visit Week 16.

⁶ In consenting subjects, colonoscopy must be performed a minimum of 8 days and a maximum of 20 days prior to visit Week 52.

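### SAP 2.2.3 ends duration of remission and of response on CDAI alone, in conflict with the SAP's own rule that rescue is treatment failure, and no end date is given for rescue

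*SAP*

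**What the plan says.** Average duration of remission and average duration of response are two of the four objectives in SAP 2.1.3; the first reads "To estimate the average duration of remission among participants".

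SAP 2.2.3 gives the arithmetic. Duration of remission is "the first date following remission at which CDAI is ≥ 150 minus the date of remission", plus one day, divided by 7. Duration of response is "the first date following response at which the reduction from baseline in CDAI is < 100 minus the date of response", with the same adjustment. Remitters who "continue to be in remission at the time of their last CDAI assessment will be censored at the date of their last CDAI assessment"; the response bullet has a matching clause. SAP 6.3.3.1 then plans Kaplan-Meier summaries and a log-rank test by parent-study treatment. Neither section mentions rescue. The protocol synopsis (Outcome Measures) defines each duration only as the time spent in that state.

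The rescue rule stands elsewhere. SAP 2.2.1 opens by classing as treatment failure "any new use of rescue medication to treat CD or increased rescue medication dose from baseline prior to any remission or response assessment". SAP 6.1.6 says that in remission or response analyses "subjects who initiate new treatment or increase concomitant medication to treat CD symptoms will be considered as treatment failures". It also says that rescued subjects "may remain on the study drug at the discretion of the investigator and continue to be assessed at all scheduled study visits". CDAI values after rescue will therefore exist.

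**The concern.** A yes/no endpoint can absorb a failure rule without a date: the subject is scored as not in remission. A duration cannot. It needs an end date and a status, event or censored. The formulas in 2.2.3 are complete without rescue, so a programmer who follows them carries a rescued subject forward for as long as the CDAI criterion is met, and then censors that subject as still in remission or response.

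The report could then disagree with itself. A subject rescued at week 30 fails week 52 remission under 2.2.1, yet the duration of remission table (Table 14.2.4.2) would show the same subject as still in remission at the last assessment.

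Rescue after an early remission is foreseeable. Steroids are to be tapered after 4 weeks of treatment with the aim of stopping by week 14, and other Crohn's therapies may be adjusted after week 8 (SAP section 3; protocol synopsis, Study Design). Steroids, immunosuppressants and biologics are all on the 6.1.6 rescue list.

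**Working it through.** The plan states no figure for this point, so there is none to reproduce. The check applies the SAP's own formula to its own visit schedule.

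**Inputs**
- Formula (SAP 2.2.3): duration in weeks = (end date − start date + 1 day) / 7. With nominal weeks *a* (start) and *b* (end), d(a,b) = [7(b − a) + 1] / 7.
- Visits (SAP 4.1.1, row "CDAI assessment"): after screening, weeks 8, 16, 26, 39, 52 and 56.
- Assumed subject: remission first seen at week *a*, new or increased rescue later, CDAI below 150 at every later visit through week 52.

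**Formula as written (censored at last CDAI)**
- Onset week 16: d(16,52) = (252 + 1)/7 = 36.1 weeks.
- Onset week 8: d(8,52) = (308 + 1)/7 = 44.1 weeks.

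**Rescue rule applied at the next CDAI assessment (event)**
- Onset 16, rescue at week 20, next visit week 26: d(16,26) = (70 + 1)/7 = 10.1 weeks.
- Onset 16, rescue at week 30, next visit week 39: d(16,39) = (161 + 1)/7 = 23.1 weeks.
- Onset 8, rescue at week 10, next visit week 16: d(8,16) = (56 + 1)/7 = 8.1 weeks.

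**Excess of the literal formula over the next-assessment rule, onset week 16**

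| Rescue between weeks | Ended at next assessment | Excess, last CDAI week 52 | Excess, last CDAI week 56 |
|---|---|---|---|
| 16 and 26 | 10.1, event | 52 − 26 = 26 weeks | 56 − 26 = 30 weeks |
| 26 and 39 | 23.1, event | 52 − 39 = 13 weeks | 56 − 39 = 17 weeks |
| 39 and 52 | 36.1, event | 52 − 52 = 0 weeks, but censored becomes event | 56 − 52 = 4 weeks |

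**Rescue date as the end instead.** Onset 16 and rescue at week 20 gives d(16,20) = (28 + 1)/7 = 4.1 weeks. Rescue at week 30 gives d(16,30) = (98 + 1)/7 = 14.1 weeks.

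The subject rescued at week 30 can therefore be recorded as 36.1 weeks censored, 23.1 weeks with an event, or 14.1 weeks with an event, depending on a choice that the SAP does not make.

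**The case against.** The strongest reply is that the SAP never says that time on rescue counts as remission, and that its drafting pattern points the other way. The week 16 remission and response definitions are also worded on CDAI and missing data alone, with the general rescue rule laid over them. That rule reaches every remission or response assessment, and the durations are remission and response analyses. On this reading a CDAI visit after rescue is a failed assessment, the subject is not still in remission at the last visit, and the last-CDAI censoring clause does not clearly apply.

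This stands in part. A reader might infer from the formulas that the SAP has decided to count rescue time as remission; 2.2.1 and 6.1.6 do not support that. But the overriding reading still leaves a gap. The subject has neither reached the CDAI end criterion nor continued in remission, and nothing says when the duration ends or whether the end is an event.

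Two further replies are fair. The worked cases are hypothetical subjects who keep a low CDAI after rescue. Rescue is given for new or unresolved symptoms, so some rescued subjects will lose remission by CDAI anyway and end under the existing formula. And these are secondary endpoints in an open-label estimation study.

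**Conclusion.** The conflict is real and should be fixed. The 2.2.3 formulas and the rescue rule in 2.2.1 and 6.1.6 give different answers for a subject who is rescued and still meets the CDAI criterion, and the SAP does not resolve the difference. Under next-assessment dating with onset at week 16 and last CDAI at week 52, the difference for such a subject is 26, 13 or 0 weeks depending on when rescue starts. In every case the status changes from censored to event. These figures assume nominal visit timing and a CDAI that stays below 150.

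Stronger conclusions might be drawn that the documents do not support:
- That the reported average durations are inflated by some amount. No rescue rate is given, so neither the number of affected subjects nor any cohort effect can be derived.
- That the parent-arm log-rank test is biased in a known direction. All subjects receive RHB-104, and rescue could occur in either parent group.
- That 6.1.6 makes a subject a failure at assessments before the rescue. Its last sentence omits the timing limit, but 2.2.1 states it and the intent is clear.
- That the main results are at risk. The week 16 primary and key secondary analyses are unaffected.

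**What to change.** In SAP 2.2.3, end duration of remission and duration of response, as an event, at the earlier of (a) loss by the CDAI criterion and (b) the first CDAI assessment after new or increased rescue. Use the rescue date if no CDAI assessment follows. Next-assessment dating matches how CDAI loss is already dated. Keep the baseline dose as the comparator for an increase.

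As clarification only:
- Cross-reference the 2.2.1 rescue rule in the time to remission, time to response and maintenance of remission bullets. For the two time-to-event endpoints, say that CDAI values after rescue do not count as a first remission or response, and that such subjects remain non-events under the existing last-CDAI censoring, not censored at rescue.
- In 6.1.6, repeat that rescue makes a subject a failure only at assessments after it.

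The cost is a few sentences and minor programming from concomitant medication and steroid records already collected. Visits, treatment and rescue care do not change. The downside is that durations for rescued subjects become shorter or change from censored to event.
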